### **Objective(s) of the Study:**

The aim of this study was to determine the immunomodulating effect of *N. sativa* on T lymphocyte cell activity, various inflammatory cytokines, and SLEDAI Score in paediatric SLE patients.

### **Study design :**

This is a clinical trial study, pre and post test control group design, that has received permission from the ethics committee of Health Research Ethics Commission General Hospital [name] Malang with number (400/089/K3/302/2021). The research design is single blind and uses a placebo group as the control.

### **Methods:**

A total of 32 SLE paediatric patients were randomly divided into two groups, the *N. sativa* oil treatment group and the placebo group. Each patient consumed 1 gram of *N. sativa* oil capsule or 1 gram of starch capsule daily for 8 weeks. *N. sativa* oil capsules were purchased from CV Rizki Abadi, Tuban, East Java, Indonesia, (POM TR.183314171). Standard therapy in all patients was Prednisone, Hydroxychloroquine, and Mycophenolate acid. Every week, the research team monitored the patients by phone to determine the progress of the patients' condition and any possible side effects.

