**Statistical analysis**

Data for each patient were collected in the form of a data collection sheet. Numerical data were analysed by Independent T Test if the data were normally distributed or by Mann-Whitney test if the data were not normally distributed. For pre and post treatment, each group (N. sativa treatment and placebo), if normally distributed using Paired T Test, but if not normally distributed using Wilcoxon test. Statistical tests were considered meaningful if the p value was  $\leq 0.05$ . All calculations were performed with the help of SPSS for Windows 25.0 software.

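### The plan describes no recording of background-drug doses or dose changes and uses none in the analysis, so a co-intervention difference could be mistaken for an N. sativa effect or hide one

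*Combined protocol and SAP*

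**What the plan says.** The objective is an effect on "T lymphocyte cell activity, various inflammatory cytokines, and SLEDAI Score in paediatric SLE patients". Under Methods, "A total of 32 SLE paediatric patients were randomly divided into two groups", one taking the oil and the other "1 gram of starch capsule daily for 8 weeks". Background treatment gets one sentence: "Standard therapy in all patients was Prednisone, Hydroxychloroquine, and Mycophenolate acid". Doses, stability of doses and the capture of changes are not mentioned there or elsewhere.

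Contact during treatment is a weekly call in which "the research team monitored the patients by phone to determine the progress of the patients' condition and any possible side effects". Medication is not named as a topic. Research Procedures lists blood sampling, T-cell subsets, cytokines and SLEDAI-2K as what is measured. On masking, Study design says only "The research design is single blind and uses a placebo group as the control".

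Statistical analysis says "Data for each patient were collected in the form of a data collection sheet" without giving the sheet's contents. It plans an independent t test or Mann-Whitney test between arms, and a paired t test or Wilcoxon test within each arm. There is no covariate, no stratification, no handling of dose changes and no sensitivity analysis.

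**The concern.** Prednisone, hydroxychloroquine and mycophenolic acid are given to control the disease activity that SLEDAI-2K scores, and they act on the immune measures that make up the other outcomes. A change in their dose during the 8 weeks therefore competes with the oil as an explanation of any result.

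Randomisation makes starting doses comparable apart from chance. It does not protect against later changes made by someone who knows the arm, and the plan does not rule that out. The within-arm tests are more exposed still: a dose change shared by both arms cancels on average in the arm comparison but not in a pre-post comparison.

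At stake is attribution in both directions. An arm difference could come from more background treatment in that arm, and a real benefit could be hidden if placebo children were stepped up more often. The planned analysis would let a reader see neither.

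**Working it through.** The documents give no effect size, SD, power or dose figure, so there is no stated figure to reproduce. What follows is an illustration.

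**Inputs**
- From Methods: 32 children, two groups, 8 weeks.
- From Statistical analysis: significance at p ≤ 0.05.
- Assumed: 16 per arm (the ratio is not stated), a two-sided test, normal outcomes with SD 1, background drugs increased in 5 of 16 children in one arm and 1 of 16 in the other, and each increase moving the outcome by e = 0.5, 1.0 or 1.5 SD.

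**Bias in the arm difference**

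Bias = (5/16 − 1/16) × e = 0.25e, which gives 0.125, 0.25 and 0.375 SD.

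**False-positive rate with no true effect** (simulated t test, 16 per arm)

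| e (SD) | Bias (SD) | Exactly 5 v 1 | Random, probabilities 5/16 v 1/16 |
|---|---|---|---|
| 0.5 | 0.125 | 6.0% | 6.3% |
| 1.0 | 0.25 | 8.2% | 9.6% |
| 1.5 | 0.375 | 11.0% | 14.3% |

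A shortcut that moves the whole arm by the bias (non-central t, 30 df, standard error √(2/16) = 0.354) gives 6%, 11% and 18%. That is too high for this scenario, because moving only some children also widens the spread. At e = 1.5 the sample variances become on average 1 + 2.25 × (5 × 11)/(16 × 15) = 1.52 and 1 + 2.25 × (1 × 15)/(16 × 15) = 1.14. The pooled SD is then about √((1.52 + 1.14)/2) = 1.15 rather than 1.

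**Masking of a true effect**

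With a true 0.8 SD effect and no step-ups, power is 59%. If 5 placebo children and 1 treated child are stepped up with e = 1.0, the expected difference is 0.8 − 0.25 = 0.55 SD, and simulated power is about 28%. The whole-arm shortcut gives 33%.

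**Within-arm tests**

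If 5 of 16 children in an arm are stepped up with e = 1.0, that arm's mean change moves by 5/16 = 0.31 SD, whatever happens in the other arm.

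**Baseline dose**

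With 16 per arm, chance gives a difference in baseline dose of at least 0.5 SD in 2 × (1 − Φ(0.5/0.354)) = 16% of randomisations. The test's error rate already allows for this, so adjustment is a matter of precision. With a partial correlation of 0.2 to 0.4 between baseline dose and outcome, power at 0.8 SD rises from 59% to between 61% and 67%.

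**The case against.** The strongest reply is that the point reads silence as fact and then builds a chain of assumptions on it. Several parts of that reply stand.

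- A reader might infer that doses are not recorded. The documents do not show that: the contents of the data collection sheet are not given, and the account of the weekly call does not say that it excluded medication. What can be said is that no recording is described and no analysis uses dose.
- A reader might infer that the result could never be untangled. The charts should hold the doses, so the information probably exists. It is simply not planned for use.
- A reader might infer that prescribers were unmasked. The plan does not say who is masked, so this is a possibility only.
- The 5 v 1 split and the size of the step-up effect are assumed. A 5 v 1 split is itself compatible with chance (Fisher p = 0.17), and chance divergence unrelated to arm is covered by the test's error rate. If placebo children need more background treatment because the oil works, that is a consequence of treatment and not a bias of this kind. Only divergence by arm for reasons other than the oil's effect produces the extra false positives.

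The reply does not remove the gap in the analysis. Even if every dose is on the sheet, the planned tests ignore it, and nothing elsewhere in the documents addresses dose changes.

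**Conclusion.** The concern holds in this form: no recording of background doses or dose changes is described, no analysis uses them, and the arm comparison and the within-arm tests are both open to co-intervention bias. It should be corrected.

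Under the assumed scenario the distortion is moderate: a false-positive rate of about 6% to 11% (6% to 14% with random step-ups) in place of 5%, and power of about 28% in place of 59% in the masking case with a 1 SD step-up effect. These figures depend on 16 per arm, the 5 v 1 split and the assumed effect per child, none of which the documents give. They show what could happen, not that it did. Chance imbalance in starting dose is a lesser matter of precision.

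**What to change.** **Data.** Take from the chart each child's doses of the three drugs at baseline and week 8, with the date and reason of every change in either direction. The text is in the past tense. If the trial is still running, add a dose line to the weekly call as well; if not, chart extraction is enough. State who is masked.

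**Main analysis.** For every outcome, replace the unadjusted between-arm test with an ANCOVA (rank-based if the data are not normal) of the week-8 value on arm, the baseline value of that outcome and baseline prednisone dose per kg. Keep all children whatever happens to their doses. Do not adjust for on-study dose, which may itself respond to treatment.

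**Supporting analyses.** Tabulate dose increases and decreases by arm beside the results. Prespecify one sensitivity analysis for SLEDAI-2K, T-cell and cytokine outcomes in which children whose background drugs were increased for disease activity take the worst ranks. Say in advance which direction counts as worst for each outcome.

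**Interpretation.** Do not attribute within-arm pre-post changes to N. sativa. Report as a limitation any arm difference whose direction is not kept in the sensitivity analysis.

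**Cost.** One chart extraction per child, two degrees of freedom, one table and one sensitivity analysis. No dose or dosing rule is proposed.

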### **Research Procedures**

#### **1. Blood Collection**

Blood samples were taken twice, at the beginning of the study and at the end of the treatment at the RSSA Clinical Pathology Laboratory by laboratory staff. The volume of blood taken in each research sample was 8 ml. Furthermore, blood samples were made serum through a centrifugation process at 3000 rpm for 5 minutes, and stored at 4°C for measurement of the patient's immunological profile.

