#### **2. Measurement of T lymphocyte cell profile**

From the peripheral blood samples obtained earlier, PBMC isolation was carried out. PBMCs were isolated using Ficoll gradient density centrifugation. The PBMC suspension was incubated overnight at 37°C in RPMI 1640 media with 100 U/mL penicillin and streptomycin, 2 mM glutamine, and 10% FBS. The PBMCs were collected, washed, and stained with fluorescein isothiocyanate-conjugated anti-human CD4. After surface labeling, cells were stained with phycoerythrin (PE)-conjugated anti-human IFN-γ to identify Th1. Th2 detection was carried out using PE-conjugated anti-human IL-4. Treg detection was performed using CD25+Foxp3-PE antibodies. Th17 identification was carried out using CD4+IL-17A-PE antibodies. All antibodies were using brands from BD Bioscience (San Jose, US).

Afterwards, the analysis was carried out using a BD FACS Calibur flow cytometer (Becton Dickinson, USA). The cell population percentages were organized and analyzed using the CELL Quest pro software application.

3. Measurement of cytokine levels

Serum levels of IFN- $\gamma$ , TNF- $\alpha$ , IL-2, IL-4, IL-6, IL-17, and IL-10 were measured at both baseline and endpoint of the trial. They were measured using commercially available cytokine CBA (Cytometric Bead Array) flow cytometry kits, which can measure multiple analytes at the same time. All antibodies were using brands from Becton Dickinson (US) and the software to analyse it was CELL Quest Pro Software from Becton Dickinson (New Jersey, USA).

4. Scoring SLEDAI

SLE disease activity was measured using SLEDAI 2K. The data required are clinical manifestations, including arthritis, fever, elevated dsDNA, and other conditions such as photosensitivity and arthralgia. Each clinical manifestation was given a score, and the scores were then summed to obtain the total SLEDAI 2K score.

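### Serum is kept at 4°C with no time-to-assay limit and no same-run rule for a patient's two samples, so within-arm cytokine changes may partly reflect handling

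*Combined protocol and SAP*

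**What the plan says.** Research Procedures, item 1 (Blood Collection): "Blood samples were taken twice, at the beginning of the study and at the end of the treatment". The serum is then "stored at 4°C for measurement of the patient's immunological profile". That is the only storage condition given. There is no duration, no freezing step and no maximum time to assay.

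Methods puts the two draws about 8 weeks apart, since capsules are taken "daily for 8 weeks".

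Research Procedures, item 3 (Measurement of cytokine levels) names seven serum cytokines: IFN-γ, TNF-α, "IL-2, IL-4, IL-6, IL-17, and IL-10". It says they "were measured at both baseline and endpoint of the trial", and on method: "They were measured using commercially available cytokine CBA (Cytometric Bead Array) flow cytometry kits". It does not say whether a patient's two samples share a run or kit lot, whether both arms appear in each run, or whether a bridging control is used.

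Statistical analysis plans a between-arm test and also a test inside each arm: "For pre and post treatment, each group (N. sativa treatment and placebo), if normally distributed using Paired T Test", with the Wilcoxon test as the alternative.

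**The concern.** A paired test attributes any systematic difference between a patient's two measurements to the passage of time on treatment. It cannot tell a biological change from a change in how the tubes were handled. With one refrigerated storage condition and no run rule, the plan leaves two handling routes open:

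- If a patient's pair is assayed together after week 8, both samples share a run, but the baseline serum has been refrigerated about 8 weeks longer.
- If each sample is assayed soon after it is drawn, storage is similar, but the two results come from different runs.

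A mixture of the two is also possible. What is at stake is the false-positive rate of the within-arm cytokine tests and, in a trial of 32 patients, the precision of the change that the between-arm comparison would use. The point covers the serum cytokines only, not the flow-cytometry cell percentages or the SLEDAI score.

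**Working it through.** **Inputs from the documents.** Total sample size: "A total of 32 SLE paediatric patients were randomly divided into two groups" (Methods). Two samples per patient, about 8 weeks apart; seven cytokines; paired t or Wilcoxon test within each arm; significance at 0.05.

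**Inputs assumed, because the documents give none.** An even split (16 per arm), two-sided tests, weekly loss at 4°C, between-run CV, SD of the log change, enrolment pattern. The plan states no power or precision figure to reproduce.

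**1. Pairs assayed together, baseline refrigerated 8 weeks longer.** With weekly loss w, the loss over 8 weeks is 1 − (1 − w)^8 and the log shift is −8 ln(1 − w). At w = 2% the loss is 14.9% and the shift 0.162. Dividing by an SD of log change of 0.8 or 0.4 gives a standardised shift of 0.202 or 0.404. Multiplying by √16 gives a noncentrality of 0.81 or 1.62. The noncentral t on 15 df then gives:

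| Weekly loss | 8-week loss | False significance, SD 0.8 | SD 0.4 |
|---|---|---|---|
| 1% | 7.7% | 6.6% | 11.7% |
| 2% | 14.9% | 11.8% | 32.8% |
| 5% | 33.7% | 48% | 97% |

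If the storage difference is one week instead of eight, the same 1–5% weekly losses give 5.0–7.7%.

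**2. Samples assayed as drawn, all baselines in one run and all endpoints in another.** Let σ² = ln(1 + CV²) be the run variance on the log scale. The run shift is common to all 16 patients and has variance 2σ², so the t statistic is inflated by √(1 + 16·2σ²/SD²).

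- CV 10%, SD 0.6: √(1 + 32 × 0.00995/0.36) = 1.37. The effective critical value is 2.131/1.37 = 1.55, and false significance is about 14%.
- CV 15%, SD 0.4: √(1 + 32 × 0.02225/0.16) = 2.33. The effective critical value is 2.131/2.33 = 0.91, and false significance is about 38%.

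**3. Samples assayed as drawn, with staggered enrolment and weekly runs.** One patient's endpoint can share a run with another's baseline, so run shifts average out. Simulated false significance over the same CV and SD ranges:

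| Enrolment period | False significance within an arm |
|---|---|
| 4 weeks | 7–15% |
| 8 weeks | 6–10% |
| 16 weeks | 5.4–6.0% |
| 26 weeks | 5.0–5.7% |

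**4. Every sample in its own run.** There is no bias and the error rate is 5%, but the variance of change is multiplied by 1 + 2 ln(1 + CV²)/SD². CV 10% with SD 0.6 gives 1.055; CV 20% with SD 0.4 gives 1.49. This is equivalent to losing 1 − 1/1.055 = 5% to 1 − 1/1.49 = 33% of the patients.

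**5. Between-arm comparison of change.** With a proportional baseline loss of 10%, 20% or 30% in both arms (20,000 simulated trials, log-SD 0.5, pre/post correlation 0.6), the within-arm test gave 12%, 40% and 78% false rises. The between-arm test stayed at 4.6–4.9%. If the shift differed between arms by 0.25 or 0.50 SD of change, between-arm error would be 10.5% or 27.8%. Noise adding 25% or 50% to the variance of change cuts 80% between-arm power to 71% or 63%.

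**The case against.** The strongest reply is that the plan shows a lack of control, not an actual distortion. Most of it stands.

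- A reader might infer that storage loss and run shift are both present in every pre/post change. The documents do not support that. They give a temperature but no duration, and the cytokine section reads at least as naturally as two assay occasions. The two mechanisms also largely trade off: assaying promptly leaves little differential storage, and assaying pairs together removes the run difference.
- A reader might infer that time point is confounded with run whenever samples are assayed as drawn. That needs baselines and endpoints to fall in separate runs. With enrolment staggered over 16 weeks or more, false significance is close to 5%. No enrolment period is given.
- A reader might take the full span in the storage table, about 7% to 97%, as the size of the problem. It rests on loss rates with no basis in the documents and on an unstated 8-week wait, so it illustrates sensitivity and is not an estimate.
- A reader might infer that the randomised comparison is biased. A shift common to both arms cancels there and would also show in the placebo arm's own paired test. Bias between arms needs arms unbalanced across runs or storage times; the plan does not prevent this, but nothing says it happened.
- Within-arm tests cannot isolate a drug effect even with perfect handling, because time, regression to the mean and standard therapy also move the values.

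The reply does not remove the point. The within-arm tests are a stated analysis, and under the plan as written a patient's two samples will differ in refrigerated storage time or in run. A better procedure is available at little cost.

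**Conclusion.** The concern holds as an uncontrolled risk to the within-arm cytokine tests and to the precision of change. It does not show that any result is distorted. Bias arises within an arm if baseline serum waits about 8 weeks longer at 4°C, or if baselines and endpoints are run separately. In other schedules run variation only adds noise. The between-arm comparison is protected from a common shift and pays in precision, unless arms are unbalanced across runs or storage times.

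Assuming 16 per arm, false significance within an arm is about 5% with prompt assay and well-staggered runs. It is 12–33% with 2% loss per week over 8 weeks (SD of log change 0.8 to 0.4), and 14–38% with one baseline run against one endpoint run (CV 10–15%, SD 0.6 to 0.4). Which case applies cannot be read from the documents.

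**What to change.** In Research Procedures, item 1, replace refrigerated storage until measurement with aliquoting and freezing the serum on the day of collection. In item 3, require that both samples from a patient be assayed in the same bead-array run, with patients from both arms in every run and the operator unaware of arm and time point. The two changes belong together: joint assay without freezing would lengthen the differential storage.

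The cost is freezer space for 64 serum samples (32 patients × 2) and a run plan. The kits and number of wells are unchanged. Cytokine results become available only after the week-8 visit.

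If samples have already been assayed separately, report storage times and run allocation by arm and time point. Base the cytokine conclusions on the between-arm comparison of change, not on the within-arm tests. Adding run as a model factor should not be relied on: with one baseline run and one endpoint run it is aliased with time, and with one run per sample it is aliased with the sample.

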#### **2. Measurement of T lymphocyte cell profile**

From the peripheral blood samples obtained earlier, PBMC isolation was carried out. PBMCs were isolated using Ficoll gradient density centrifugation. The PBMC suspension was incubated overnight at 37°C in RPMI 1640 media with 100 U/mL penicillin and streptomycin, 2 mM glutamine, and 10% FBS. The PBMCs were collected, washed, and stained with fluorescein isothiocyanate-conjugated anti-human CD4. After surface labeling, cells were stained with phycoerythrin (PE)-conjugated anti-human IFN-γ to identify Th1. Th2 detection was carried out using PE-conjugated anti-human IL-4. Treg detection was performed using CD25+Foxp3-PE antibodies. Th17 identification was carried out using CD4+IL-17A-PE antibodies. All antibodies were using brands from BD Bioscience (San Jose, US).

Afterwards, the analysis was carried out using a BD FACS Calibur flow cytometer (Becton Dickinson, USA). The cell population percentages were organized and analyzed using the CELL Quest pro software application.

3. Measurement of cytokine levels

Serum levels of IFN- $\gamma$ , TNF- $\alpha$ , IL-2, IL-4, IL-6, IL-17, and IL-10 were measured at both baseline and endpoint of the trial. They were measured using commercially available cytokine CBA (Cytometric Bead Array) flow cytometry kits, which can measure multiple analytes at the same time. All antibodies were using brands from Becton Dickinson (US) and the software to analyse it was CELL Quest Pro Software from Becton Dickinson (New Jersey, USA).

4. Scoring SLEDAI

SLE disease activity was measured using SLEDAI 2K. The data required are clinical manifestations, including arthritis, fever, elevated dsDNA, and other conditions such as photosensitivity and arthralgia. Each clinical manifestation was given a score, and the scores were then summed to obtain the total SLEDAI 2K score.

**Ethical clearance:**

Please find attached

**Statistical analysis**

Data for each patient were collected in the form of a data collection sheet. Numerical data were analysed by Independent T Test if the data were normally distributed or by Mann-Whitney test if the data were not normally distributed. For pre and post treatment, each group (N. sativa treatment and placebo), if normally distributed using Paired T Test, but if not normally distributed using Wilcoxon test. Statistical tests were considered meaningful if the p value was  $\leq 0.05$ . All calculations were performed with the help of SPSS for Windows 25.0 software.

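### The between-arm comparison names no response (end-of-treatment value or change) and leaves the collected baseline values unused; naming the response closes the choice, and ANCOVA usually adds precision

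*Combined protocol and SAP*

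**What the plan says.** All references are to the combined protocol and SAP. Week 8 is shorthand here for the end of the 8-week treatment.

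- **Between-arm test** (Statistical analysis): "Numerical data were analysed by Independent T Test if the data were normally distributed or by Mann-Whitney test", the latter when normality fails. No response variable and no covariate is named.
- **Within-arm test** (same section): "For pre and post treatment, each group (N. sativa treatment and placebo), if normally distributed using Paired T Test", otherwise Wilcoxon. These tests set pre against post inside each group. They do not compare the arms, and they do not settle what the between-arm test is applied to.
- **Threshold** (same section): "Statistical tests were considered meaningful if the p value was" 0.05 or less. Sidedness is not stated.
- **Baseline data.** The Study design section describes a "pre and post test control group design". Under Blood Collection, "Blood samples were taken twice, at the beginning of the study and at the end of the treatment", which covers the four T-cell subsets. The cytokine item says that the seven serum levels "were measured at both baseline and endpoint of the trial". The Scoring SLEDAI item gives no timing, so a baseline SLEDAI-2K is implied only by the pre/post design.
- **Size** (Methods): "A total of 32 SLE paediatric patients were randomly divided into two groups". The number per group is not given. No effect size, SD, correlation or target power is given anywhere.

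**The concern.** With one baseline and one end-of-treatment measurement, the arms can be compared on the week-8 value, on the change, or on the week-8 value adjusted for baseline. The plan rules out none of the first two and does not mention the third.

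Two things follow. First, the week-8 and change comparisons are different tests on the same data and often disagree, so an unnamed response lets the conclusion depend on a choice that a reader cannot see. Second, each unadjusted test is imprecise in part of the plausible range: the change comparison when baseline and week-8 values are weakly correlated, the week-8 comparison when they are strongly correlated. With 32 patients, precision is scarce, and the information that would improve it is already being collected.

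**Working it through.** The plan gives no sample-size or power figure, so there is nothing to reproduce.

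**Inputs.** From the document: 32 patients in total, threshold 0.05. Assumed: 16 per arm, two-sided test, normal data, SD of 1 at both visits, no dropout, true effect 0.8 SD, and correlation r between baseline and week 8 taken over a range.

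**Variance of the estimated arm difference.** The base is 2/16 = 0.125.

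- Week-8 value: 0.125, at any r.
- Change: 0.125 × 2(1 − r).
- ANCOVA: 0.125 × (1 − r²) × 29/28, where 29/28 = 1 + 1/(32 − 4) allows for chance baseline imbalance.

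At r = 0.5 these are 0.125, 0.125 × 1 = 0.125, and 0.125 × 0.75 × 29/28 = 0.0971. Dividing 0.8 by the square roots gives noncentrality 2.263, 2.263 and 2.567.

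**Power.** Noncentral t, 30 degrees of freedom (29 for ANCOVA):

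| r | Week-8 | Change | ANCOVA | ANCOVA minus better | ANCOVA minus worse |
|---|---|---|---|---|---|
| 0 | 59.1% | 34.1% | 57.5% | −1.6 | +23.4 |
| 0.2 | 59.1% | 41.0% | 59.2% | +0.1 | +18.3 |
| 0.3 | 59.1% | 45.7% | 61.5% | +2.4 | +15.9 |
| 0.5 | 59.1% | 59.1% | 69.9% | +10.8 | +10.8 |
| 0.7 | 59.1% | 80.7% | 85.3% | +4.6 | +26.2 |
| 0.8 | 59.1% | 93.3% | 94.7% | +1.4 | +35.6 |
| 0.9 | 59.1% | 99.8% | 99.8% | 0.0 | +40.8 |

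Differences are in percentage points and were taken before rounding. In variance, ANCOVA breaks even with the week-8 test at r = 0.19. A simulation of 40,000 trials at r = 0.5 gave 59.1%, 58.8% and 70.0%.

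**Sensitivity.** Gain over the better unadjusted test at r = 0.3, 0.5 and 0.7: +1.3, +6.4, +4.5 for a 0.5 SD effect; +2.3, +9.2, +2.2 for 1.0 SD; +2.4, +10.7, +4.8 for 0.8 SD with a 20:12 split.

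**Leaving the response open.** In 200,000 simulated null trials per r, counting a trial as positive if either t-test has p ≤ 0.05, type I error was 8.4%, 8.9%, 9.1%, 9.4% and 9.7% at r = 0, 0.3, 0.5, 0.7 and 0.9. Repeat runs move these by a tenth or two of a point, so about 8.5% to 9.7%. With a true 0.8 SD effect, exactly one of the two tests was significant in 32% to 41% of trials.

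**Why ANCOVA removes this choice.** Change is the week-8 value minus baseline. With baseline in the model, switching between the two responses, on the same scale, only lowers the baseline coefficient by 1; the arm estimate and its p value are identical.

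**Skewed outcomes.** One assumed case: lognormal data, log-SD 1, arm shift 0.8 on the log scale, log-scale r = 0.5, 40,000 trials. Power was 55.9% for Mann-Whitney on week-8 values, 57.3% for Mann-Whitney on raw change, 70.2% for log-scale ANCOVA, 66.7% for rank ANCOVA and 47.7% for untransformed ANCOVA. The scale therefore matters as much as the adjustment.

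**The case against.** The strongest reply is that only the unnamed response is a defect. Either unadjusted test is valid under randomisation once its response is fixed, and the absence of ANCOVA is an efficiency choice whose size cannot be known here, because the document gives no correlation, effect size or SD. This stands, and it is why naming the response is the minimum fix and ANCOVA the preferred one.

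A reader might infer that ANCOVA never costs power. The document does not support that: nothing in it excludes r below about 0.2, where ANCOVA is slightly worse than the week-8 test. The gain near 11 points also belongs to r near 0.5 with an effect near 0.8 SD.

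A reader might also infer that the trial's error rate is in fact inflated, or that the favourable response was picked. Nothing in the document shows that both comparisons were made. The figure of 8.5% to 9.7% is conditional on that, and was computed for t-tests on normal data, not for Mann-Whitney or for an integer score such as SLEDAI-2K.

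Finally, ANCOVA can bring back a choice if its scale is picked from the data. In a lognormal null simulation with 16 per arm (r = 0 to 0.7), taking the better of untransformed and rank ANCOVA gave 6.5% to 7.4% type I error. Blinding is not a sure safeguard: the plan says "The research design is single blind and uses a placebo group as the control" but not who is blinded. This stands too, so the scale has to be assigned beforehand.

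**Conclusion.** The point holds as a specification gap with a cheap improvement attached. It does not show that the planned tests are invalid. That the plan names neither response nor covariate is certain from the text.

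The sizes are conditional on the assumptions listed in the working. Over the better unadjusted test, ANCOVA gains about 0 to 11 power points for r of about 0.2 to 0.9 and loses up to 1.6 points below about 0.2. Over the worse one, the gain at 0.8 SD is 10.8 to 40.8 points across the r values tabulated; since the plan leaves the response open, either test could be the one used. This should be corrected, but it would not by itself overturn the trial.

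**What to change.** **Minimum.** Name one response, week-8 value or change, for each outcome.

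**Preferred.** Replace the between-arm sentence in the Statistical analysis section with text to this effect:

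- For each outcome, the arms are compared by ANCOVA with the week-8 value as response, arm as factor and the baseline value of the same outcome as covariate. The scale of each outcome is fixed in advance and not chosen from the data.
- Cytokines: log scale, reported as the adjusted ratio of geometric means with 95% CI, with one stated rule for undetectable values.
- T-cell percentages and SLEDAI-2K: each assigned in advance either to untransformed ANCOVA (adjusted difference with 95% CI) or to rank ANCOVA (p value, with medians by arm and visit, because rank ANCOVA gives no difference in the outcome's units).
- SLEDAI-2K is scored at baseline and at week 8.

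**Cost.** No new visits, samples or patients. ANCOVA uses one degree of freedom and loses up to about 1.6 power points if r is near 0.

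**If the data have already been analysed.** The past tense of the Methods, Research Procedures and Statistical analysis sections suggests this. New SAP text cannot then remove selection. Disclose which response the planned tests used, and report the ANCOVA as post hoc beside them.
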